5.7.6 Patient Follow-up

The 30-day follow-up of patient data will be presented in data listings for the safety population.

6 CHANGES IN THE CONDUCT OF THE STUDY OR PLANNED ANALYSES

6.1 Analysis of Pharmacokinetic Data

Not applicable

6.1.1 Drug-drug and Drug-disease Interactions

There will be no analyses of drug-drug or drug-disease interactions.

6.2 Changes in the Conduct of the Study

Any changes in the conduct of the study after approval of this analysis plan, which may impact analyses performed, will require a revision of this analysis plan prior to database lock.

6.3 Changes from the Analyses Planned in the Protocol

Any changes from the analyses planned in the protocol and not discussed in the analysis plan will be presented in the clinical study report.

7 STATISTICAL/ANALYTIC ISSUES

7.1 Adjustments for Covariates

There will be no adjustments for covariates.

7.2 Handling of Dropouts or Missing data

Missing values will not be imputed with the exception of analyses involving partial dates and the data obtained at early termination visits.

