- *Descriptive statistics:* n, mean, standard deviation (SD), median, minimum (min), and maximum (max)

Handling of Outliers:

For analysis purposes an outlier is defined to be an observed value which is known to be the result of an obvious error, or an observed value beyond medical reasoning. No outliers will be excluded from any analyses. The analysis may be repeated, however, by excluding any potential outliers (i.e. a sensitivity analysis performed).

Missing Dates for Adverse Events:

For partial AE dates, the non-missing parts of the partial dates will be used to determine if an AE occurred prior to the first dose of Replagal. Unless the non-missing parts are *unambiguously* before or after the first Replagal, it will always be assumed that the AE occurred after the first Replagal dose.

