5.7 Analysis of Safety

5.7.1 Adverse Events

Adverse events will be coded using the Medical Dictionary for Regulatory Activities (MedDRA) central coding dictionary, version 13.1 or higher, and will be tabulated by cohort, previous SRT status, age group and overall based on the safety population. .

Pre-treatment AEs are any AEs that occur from the time the patient has signed informed consent until prior to the first study drug infusion.

Treatment-emergent adverse events (TEAEs) will be defined as those events that occurred or worsened in severity after first treatment with Replagal AF until 30 days after the last dose.

Infusion-related reactions (IRRs) will be defined as an AE that 1) begins either during or within 12 hours after the start of the infusion and 2) is judged as possibly or probably

related to study drug. AEs that are considered IRRs will be noted as such in the appropriate field on the CRF.

A serious AE (SAE) is any AE occurring at any dose that results in any of the following outcomes:

- Death
- Is life-threatening
- Require hospitalization
- Requires prolongation of existing hospitalization
- A persistent or significant disability or incapacity
- A congenital anomaly or birth defect

Important medical events that may not result in death, be life-threatening, or require hospitalization may be considered an SAE when, based upon appropriate medical judgment, they may jeopardize the patient and may require medical or surgical intervention to prevent one of the outcomes listed in this definition.

TEAEs will be summarized by system organ class (SOC) and preferred term (PT). The total number of TEAEs by SOC and PT, as well as the number and proportion of patients experiencing a TEAE will be tabulated; a patient will be counted only once within each SOC and PT. TEAEs by SOC and PT will be tabulated by severity. In the case of multiple occurrences of the same TEAE (at the PT level) in an individual patient, the TEAE that is classified as the most severe (i.e., maximum severity) will be identified for the analysis by severity. In addition, TEAEs by SOC and PT will be tabulated by relationship to study drug by reporting the episode with the closest relationship to study drug.

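### Under SAP 7.2 a TEAE with blank causality is left out of the related-event counts and, unless the CRF field governs, out of the IRR counts

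*SAP*

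**What the plan says.** SAP 7.2 sets one rule for all variables: "Missing values will not be imputed with the exception of analyses involving partial dates and the data obtained at early termination visits". The only rule specific to incomplete AE data is in SAP 5.1 and concerns partial dates. Unless the known parts clearly place the event before or after the first dose, "it will always be assumed that the AE occurred after the first Replagal dose".

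SAP 5.7.1 uses causality in two places:

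- An IRR must satisfy two conditions, one on timing and one on causality: it "begins either during or within 12 hours after the start of the infusion and 2) is judged as possibly or probably" (the two positive categories of protocol Table 6-2). The section adds that "AEs that are considered IRRs will be noted as such in the appropriate field on the CRF".
- For the causality tables, "TEAEs by SOC and PT will be tabulated by relationship to study drug by reporting the episode with the closest relationship to study drug".

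For severity, when a patient has repeated episodes of a preferred term, "the TEAE that is classified as the most severe (i.e., maximum severity) will be identified for the analysis by severity".

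Neither SAP 5.7.1 nor protocol 7.5 says what happens to an event with no relationship or no severity recorded. Protocol Table 6-2 offers three relationship categories (not, possibly and probably related) and none for unknown. The protocol does require causality for every AE (6.10.1.2) and a severity grade for every AE (6.10.2).

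**The concern.** Safety is the study's only objective, and SAP 1.2 says these analyses go into regulatory submissions. Related events and IRRs are among the results a reader will look for first. Both depend on an investigator judgement being present in the database. Where it is absent, the plan's rule is to leave it absent, and the event then cannot enter either count on the strength of its causality.

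The SAP is also inconsistent in direction. Doubt about an AE's date is settled by assuming it came after treatment began. Doubt about an AE's cause has no such protection.

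The IRR tables are broken down by cohort, previous treatment status, age group, sex, and ADA and NAb status. Any loss carries into those strata, where one patient is a larger share of the denominator. The documents do not give the stratum sizes.

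**Working it through.** **Inputs.** Minimum 60 and up to 200 patients (SAP 3.1). Event frequency 5% and detection probability of at least 95% (SAP 3.6). The rules are those in SAP 5.1, 5.7.1 and 7.2. The documents give no fraction of AEs with missing causality, so any value for it below is an assumption.

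**Step 1. Reproduce the plan's figure.** P(at least one event) = 1 − (1 − 0.05)^60 = 0.9539, which agrees with the stated 95% or more.

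**Step 2. Follow a blank through the rules.**

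- *Single TEAE, onset inside the 12-hour window, relationship blank.* The timing criterion is met and the causality criterion is not, so the event is not an IRR under the two-part definition. If the CRF field is marked and is taken to govern, it stays in.
- *Two episodes of one preferred term, one recorded as not related and one blank.* No recorded episode is possibly or probably related. Whether the table shows the patient as not related or in a separate missing row, the patient is not in the related count.
- *Two episodes, one possibly related and one blank.* The patient is counted as related with or without a rule for blanks. A patient is lost only when every qualifying episode lacks a causality entry.
- *Severity blank.* Severity is not part of the IRR definition or of the relationship classification. A blank grade on a TEAE therefore removes nothing from either count; it affects the severity tables.

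**Step 3. Size per patient.** 1/60 = 1.7 percentage points; 1/200 = 0.5 percentage points.

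**Step 4. Size for an assumed missing share.** Let m be the share of patients with a related event of true frequency 5% who have no causality entry on any qualifying episode. The counted rate is 5% × (1 − m).

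| Assumed m | Counted rate | Expected of 60 | Expected of 200 |
|---|---|---|---|
| 0 | 5.00% | 3.00 | 10.0 |
| 5% | 4.75% | 2.85 | 9.5 |
| 10% | 4.50% | 2.70 | 9.0 |
| 20% | 4.00% | 2.40 | 8.0 |

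**Step 5. Detection, by analogy only.** Applying the SAP 3.6 formula to an event type that needs a causality call gives 1 − (1 − 0.05(1 − m))^60. This is 94.6% at m = 5%, 93.7% at 10% and 91.4% at 20%. The lowest frequency giving 95% at 60 patients is 1 − 0.05^(1/60) = 4.87%, so the tolerable m is 1 − 0.0487/0.05 = 2.6%. With 200 patients and m = 20%, the chance is 1 − 0.96^200 = 99.97%.

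**The case against.** The best reply is that SAP 7.2 only declines to impute. It does not say that such events are dropped, and a blank could be shown in a missing row without breaching it. That is right about display. It does not rescue the counts, because an event in a missing row is still not counted as related and still lacks the judgement the IRR definition asks for.

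A second reply is that blanks should be rare. Besides the recording requirements, the investigator signs the CRF after all data are captured (protocol 6.18), CRFs are reviewed for completeness (protocol 6.19) and data review meetings precede lock (SAP 7.3). All AEs are listed by patient, so gaps stay visible. This stands, and it limits the size. None of it says how a remaining blank is tabulated.

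Third, counting a blank as related may overstate risk if the event was truly unrelated, and it departs from an IRR definition based on the investigator's judgement (protocol 7.5). This also stands, and is the reason to report the counts without the assignment alongside.

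Several stronger readings are tempting and are not supported:

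- *The SAP 3.6 property fails.* That statement concerns an AE of a given type. All-causality TEAE and SAE counts need no causality entry, so it is untouched; Step 5 is an analogy. Its m also counts patients, not events. With two independent episodes each and 10% of entries missing, 0.10 × 0.10 = 1% of patients are lost, and the chance at 60 is 1 − (1 − 0.0495)^60 = 0.9525.
- *Missing severity lowers the IRR or related counts.* It does not.
- *The plan ranks a missing grade below every recorded grade.* The SAP does not state where a blank sits under maximum severity. Reporting the lower recorded grade would be a programming default, not plan text.
- *Home infusion causes missing causality.* Nothing in the documents links the two; the investigator assigns relationship wherever the infusion is given.

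**Conclusion.** The point holds for causality. Followed as written, SAP 7.2 and 5.7.1 leave a TEAE with blank relationship out of the related counts. They also leave it out of the IRR counts unless the CRF field is taken to govern, a question the SAP leaves open. Compared with the conservative handling already adopted for AE dates, the effect can only be downward. It does not follow that true risk is understated, since some unjudged events will be unrelated.

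The conclusion assumes that some causality entries are still blank at lock. Their number is unknown and, given the collection and cleaning steps, probably small. If there are none, no result changes. For severity, the point is only that the display of a blank is undefined. Overall this is a modest gap that is cheap to close in the trial's only objective.

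**What to change.** Before database lock, amend SAP 7.2 and 5.7.1 as follows:

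- Add AE relationship to the exceptions. A TEAE with missing relationship is counted as related in the related-TEAE summaries.
- Count such a TEAE as an IRR if its onset is during, or within 12 hours after the start of, an infusion, or if it is flagged as an IRR on the CRF.
- Footnote the number of events so assigned, give the counts without the assignment as a sensitivity analysis, and leave the listings as recorded.
- Show missing severity in its own row, so that it does not default to the lower recorded grade. Assigning a fixed grade is not needed.

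The assignment is to related as such. It need not place an event in the probably related category, which Table 6-2 reserves for events meeting further conditions.

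The cost is a few sentences in the SAP and a few lines of code, using data already collected. The downside is that related-TEAE and IRR rates may be slightly less favourable.

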7.3 Interim Analyses and Data Monitoring

All final planned analyses per protocol and this SAP will be performed only after the last patient has completed the study and the database has been locked. Several data review meetings will be held prior to database lock to allow ongoing safety review and clinical data cleaning and completion of final analyses.

One interim analyses were performed in 2015 for the purposes of evaluating the safety of Replagal AF in Canadian patients with Fabry disease, in order to support the safety profile of Replagal AF. Patients who enrolled and received at least 1 dose (full or partial) of Replagal on or before 04 November 2012, and have been in the study for 24 months or withdrew prematurely from the study as of 03 November 2014, were included in this interim analysis. This interim analysis was for safety purposes; the primary analysis endpoints were safety endpoints, including adverse event (AE), treatment emergent AE (TEAE), serious AE (SAE), AE leading to discontinuation of the study, infusion-related AE, and antibody status. The safety interim results were distributed to the Shire clinical trial team.

7.4 Multicenter Studies

Although this is a multi-center study, patient enrollment varies greatly among the sites so that grouping at the site level is impractical. Therefore, the statistically analysis will not be performed at the site level. However, selected data might be summarized by site or geographical region if deemed necessary.

7.5 Multiple Comparisons and Multiplicity

As there is only one group of patients in the study, no multiplicity adjustment is needed.

7.6 Examination of Subgroups and Interactions

All analyses will be performed overall and by cohort. Additionally, as specified above, selected analyses will also be performed by previous ERT status, and/or age group.

There are no planned analyses involving interactions.

7.7 Sensitivity Analysis

For analysis purposes, an outlier is defined to be an observed value which is known to be the result of an obvious error, or an observed value beyond medical reasoning. No outliers will be excluded from the main analysis. A sensitivity analysis may be performed by excluding any potential outliers.

Appendix 1 Schedule of Events for Cohort 1 (EOW Replagal Dosing Regimen)

Evaluation	Within 6 Months Prior to First Dose	Treatment Period		End of Study (30 days after last dose)
		Dosing Every Other Week (± 5 days)	Biannual/Annual Visits to Site ^a	
Informed Consent	X			
Treatment Protocol Entry Criteria	X			
Medical History	X			
Demographics	X			
Disease and Treatment History	X			
Physical Examination ^b	X		X	
Height ^f and Weight	X ^e		X	
Vital Signs ^c		X	X	
Blood Tests ^d	X		X	
Serum Anti-agalsidase alfa Antibody	X		X	
Drug Administration		X	X	
AE Assessment		X	X	X

Abbreviations: AE = adverse event; CFDI = Canadian Fabry Disease Initiative; EOW=every other week

^a Biannual or annual visits, as applicable, are intended to coincide with visits in the Canadian Fabry Disease Initiative (CFDI) protocol. Procedures and study assessments during these visits will be performed at the clinical site. For patients receiving home infusions, the infusions given at the biannual visits may be administered at the clinical site.

^b Physical examination includes assessments of head, neck, and thyroid; eyes, ears, nose, and throat; chest and lungs; heart; lymph nodes; abdomen; anorectal; genitourinary; skin; musculoskeletal; endocrine; neurological; and other.

^c Include blood pressure, pulse, respiratory rate, and temperature. Vitals signs are taken immediately before and immediately after every infusion (± 10 minutes).

^d Includes creatinine, glucose, urea, potassium, sodium, chloride, bicarbonate and fasting lipids profile.

^e Subject weight should be obtained within 1 month prior to the first infusion

^f Height measured at baseline for all patients, and for patients <18 years at baseline height will also be measured at biannual safety visits until they are ≥ 18 years of age.

Appendix 2 Schedule of Events for Cohort 2 (Weekly Replagal Dosing Regimen for Patients who Participated in REP001a)

Evaluation	Within 6 Months Prior to First Dose	Treatment Period		End of Study (30 days after last dose)
		Dosing Every Week (± 2 days)	Biannual/Annual Visits to Site ^a	
Informed Consent	X			
Treatment Protocol Entry Criteria	X			
Medical History	X			
Demographics	X			
Disease and Treatment History	X			
Physical Examination ^b	X		X	
Height ^f and Weight	X ^c		X	
Vital Signs ^c		X	X	
Blood Tests ^d	X		X	
Serum Anti-agalsidase alfa Antibody	X		X	
Drug Administration		X	X	
AE Assessment		X	X	X

Abbreviations: AE = adverse event; CFDI = Canadian Fabry Disease Initiative

^a Biannual or annual visits, as applicable, are intended to coincide with visits in the Canadian Fabry Disease Initiative (CFDI) protocol. Procedures and study assessments during these visits will be performed at the clinical site. For patients receiving home infusions, the infusions given at the biannual visits may be administered at the clinical site.

^b Physical examination includes assessments of head, neck, and thyroid; eyes, ears, nose, and throat; chest and lungs; heart; lymph nodes; abdomen; anorectal; genitourinary; skin; musculoskeletal; endocrine; neurological; and other.

^c Include blood pressure, pulse, respiratory rate, and temperature. Vitals signs are taken immediately before and immediately after every infusion (± 10 minutes).

^d Includes creatinine, glucose, urea, potassium, sodium, chloride, bicarbonate and fasting lipids profile.

^e Subject weight should be obtained within 1 month prior to the first infusion.

^f Height measured at baseline for all patients, and for patients <18 years at baseline height will also be measured at biannual safety visits until they are ≥ 18 years of age.
